5.4.1. Recommended Dose Modifications for PF-05082566

Every effort should be made to administer PF-05082566 on the planned dose and schedule.

In the event of significant toxicity, dosing may be delayed and/or reduced as described below. In the event of multiple toxicities, dose modification should be based on the worst toxicity observed. Patients are to be instructed to notify Investigators at the first occurrence of any adverse symptom.

Dose modifications may occur in 2 ways:

- Between cycles: next cycle administration may be delayed due to persisting toxicity when a new cycle is due to start;
- In the next cycle: dose reduction may be required in a subsequent cycle based on toxicity experienced in the previous cycle.

5.4.2. Dosing Interruptions for PF-05082566

Patients experiencing a DLT according to the definitions provided in [Section 3.4](#) or intolerable Grade 2 toxicity should have their treatment interrupted (Note for Portion B: AEs attributed to rituximab only do not meet the DLT definition).

Appropriate follow up assessments should be done until adequate recovery occurs as assessed by the Investigator. Criteria required before treatment can resume are described in [Section 5.4.3](#).

Doses may be held as needed until toxicity resolution. Depending on when the AE resolves, a treatment interruption may lead to delay the initiation of the subsequent cycle.

The need for a dose reduction at the time of treatment resumption should be based on the criteria defined in [Section 5.4.4](#), unless expressly agreed otherwise following discussion between the Investigator and the Sponsor.

In the event of a treatment interruption for reasons other than treatment-related toxicity (eg, elective surgery) lasting >8 weeks, treatment resumption will be decided in consultation with the Sponsor.

5.4.3. Dose Delays for PF-05082566

A new cycle of treatment may begin only if:

- ANC $\geq 500/\mu\text{L}$;
- Platelet count $\geq 50,000/\mu\text{L}$;
- Non-hematologic toxicities have returned to baseline or Grade ≤ 1 severity (or, at the investigator discretion, Grade ≥ 2 if not considered a safety risk for the patient).

Note: withhold scheduled dose for liver function test related AEs (including asymptomatic) Grade ≥ 3 until return to baseline or Grade ≤ 1 severity. In cases of potential liver injury, see [Section 8.5.2](#). In such cases, consultation with a hepatologist should be considered in the decision to initiate treatment with anti-inflammatory medications.

If the above conditions are not met, treatment must be delayed. If, within 8 weeks all toxicities have recovered within the limits described above, treatment with PF-05082566 can be resumed. If persisting toxicity does not allow for the resumption of treatment after 8 weeks of delay, the patient will be permanently discontinued from study treatment.

5.4.4. Dose Modifications for PF-05082566

Following dosing interruption or cycle delay due to toxicity (see [Section 5.4.2](#) and 5.4.3), the PF-05082566 dose may need to be reduced when treatment is resumed.

No specific dose adjustments are recommended for Grade 1/2 treatment-related toxicity. However, investigators should always manage their patients according to their medical judgment based on the particular clinical circumstances.

Patients experiencing recurrent and intolerable Grade 2 toxicity may resume dosing at the next lower dose level, if possible, once recovery to Grade ≤ 1 or baseline is achieved.

Patients experiencing an AE meeting the DLT definition (see [Section 3.4](#) for DLT definition) may resume dosing at the next lower dose level, if possible, once adequate recovery is achieved (see [Section 5.4.3](#)).

Dose reduction of PF-05082566 by 1 and, if needed, 2 dose levels (Table 11) will be allowed depending on the type and severity of toxicity encountered. Patients requiring more than 2 dose reductions will be permanently discontinued from the study treatment and entered into the follow-up phase. Once a patient has a dose reduction of PF-05082566 for a PF-05082566 related toxicity, the dose will not be re-escalated. All dose modifications and adjustments must be clearly documented in the patient's source notes and CRF.

Patients treated with PF-05082566 at 0.24 mg/kg requiring a dose reduction should be permanently withdrawn from study treatment.

Table 11. Available Dose Levels for PF-05082566 (mg/kg)

1.2
0.6
0.24

5.5. Investigational Product Storage

The investigator, or an approved representative, eg, pharmacist, will ensure that all investigational products, including any comparator and/or marketed products, are stored in a secured area with controlled access under required storage conditions and in accordance with applicable regulatory requirements.

Investigational products should be stored in their original containers and in accordance with the labels. See the IP manual, package insert, or equivalent for storage conditions of the product once reconstituted and/or diluted. Any storage conditions stated in the SRSD will be superseded by the storage conditions stated on the product label.

Site systems must be capable of measuring and documenting (for example, via a log), at a minimum, daily minimum and maximum temperatures for all site storage locations (as applicable, including frozen, refrigerated, and/or room temperature products). This should be captured from the time of investigational product receipt throughout the study. Even for continuous monitoring systems, a log or site procedure that ensures active evaluation for excursions should be available. The intent is to ensure that the minimum and maximum temperature is checked each business day to confirm that no excursion occurred since the last evaluation and to provide the site with the capability to store or view the minimum/maximum temperature for all nonworking days upon return to normal operations. The operation of the temperature monitoring device and storage unit (for example, refrigerator), as applicable, should be regularly inspected to ensure they are maintained in working order.

Any excursions from the product label storage conditions should be reported to Pfizer upon discovery. The site should actively pursue options for returning the product to the storage conditions described in the labeling, as soon as possible. Deviations from the storage requirements, including any actions taken, must be documented and reported to Pfizer.

Once an excursion is identified, the investigational product must be quarantined and not used until the Pfizer provides permission to use the investigational product. It will not be considered a protocol deviation if Pfizer approves the use of the investigational product after the temperature excursion. Use of the investigational product prior to Pfizer approval will be considered a protocol deviation.

Specific details regarding information the site should report for each excursion will be provided to the site.

Receipt of materials, door opening and closing, and other routine handling operations where the products are briefly out of the temperature range described in the labeling are not considered excursions.

5.6. Investigational Product Accountability

The investigator site must maintain adequate records documenting the receipt, use, loss, or other disposition of the investigational product supplies. All investigational products will be accounted for using a drug accountability form/record.

5.6.1. Destruction of Investigational Product Supplies

The sponsor or designee will provide guidance on the destruction of unused investigational product (eg, at the site). If destruction is authorized to take place at the investigator site, the investigator must ensure that the materials are destroyed in compliance with applicable environmental regulations, institutional policy, and any special instructions provided by Pfizer, and all destruction must be adequately documented.

5.7. Concomitant Medication(s)

Concomitant treatment considered necessary for the patient's well being may be given at discretion of the treating physician.

All concomitant medications, blood products, as well as interventions (eg, paracentesis, etc.) received by patients from screening until the end of study visit will be recorded on the CRF.

5.7.1. Other Anticancer or Experimental Drugs

No additional anticancer therapy will be permitted while patients are receiving study therapy.

Additionally, the concurrent use of vitamins or herbal supplements should be considered with caution.

Palliative and supportive care for disease related symptoms may be administered at the Investigator's discretion.

5.7.2. Supportive Care

Palliative and supportive care for disease related symptoms may be administered at the Investigator's discretion and according to any available American Society of Clinical Oncology (ASCO) guidelines.

5.7.3. Hematopoietic Growth Factors

The use of hematopoietic growth factors is at the discretion of the treating physician in line with local guidelines. Erythropoietin* may be used at the investigator's discretion for the supportive treatment of anemia.

*Use of erythropoietin for the treatment of anemia with cancer patients is not approved in Japan.

5.7.4. Anti-Inflammatory Therapy

Anti-inflammatory or narcotic analgesic may be offered as needed. Systemic anti-inflammatory therapies may be used to treat SAEs potentially related to the study drug. However, in such cases it is suggested that Investigators consult with a specialist based on the involved organ systems before instituting treatment.

5.7.5. Corticosteroids

Chronic, systemic corticosteroid use for palliative or supportive purpose, except for the use of systemic corticosteroids according to the rituximab prescribing information, is not permitted. Use of corticosteroids as symptomatic treatment may be allowed on individual basis and upon discussion with the Sponsor. Acute emergency administration, topical applications, inhaled sprays, eye drops or local injections of corticosteroids are allowed. Physiologic use for replacement in cases of adrenal insufficiency at doses equivalent to ≤ 10 mg of prednisone daily is acceptable.

5.7.6. Surgery

Caution is advised on theoretical grounds for any surgical procedures during the study. The appropriate interval of time between surgery and PF-05082566 required to minimize the risk of impaired wound healing and bleeding has not been determined. Stopping PF-05082566 is recommended at least 14 days prior to surgery. Postoperatively, the decision to reinitiate PF-05082566 treatment should be based on a clinical assessment of satisfactory wound healing and recovery from surgery.

5.7.7. Radiation Therapy

Palliative radiotherapy to specific sites of disease is permitted if considered medically necessary by the treating physician. All attempts should be made to rule out disease progression in the event of increased localized pain. If palliative radiotherapy is needed to control bone pain, the sites of bone disease should be present at baseline, otherwise, bone pain requiring radiotherapy will be considered as a sign of disease progression.

6. STUDY PROCEDURES

For screening, treatment period and follow-up procedures, see Schedule of Activities (Table 1-7).

For the treatment period discussed below, where multiple procedures are scheduled at the same nominal time point(s) relative to dosing, the following prioritization of events should be adhered to, where possible, in order of the most important to the least important:

- CCI [REDACTED]
- Pharmacokinetic blood specimens - obtain at the scheduled time.
- ECGs – obtain as close as possible to the scheduled time, but prior to PK blood specimen collection and within 30 minutes of the nominal time.
- Blood pressure/pulse rate – may be obtained prior to or after ECG collection but must be obtained prior to PK blood specimen collection and within 60 minutes of the nominal time.
- Clinical safety lab tests – obtain as close as possible to the scheduled time.
- Other procedures – All other procedures should be obtained as close as possible to the scheduled time, but may be obtained before or after blood specimen collection, unless sampling is determined by the study personnel to potentially impact the results.

6.1. Screening

For screening procedures see Schedule of Activities (Table 1-7).

6.2. Treatment Period

For treatment period procedures, see Schedule of Activities (Table 1-7).

6.3. Follow-up Visit

Patients whose disease has not progressed at the end of treatment will enter into disease follow-up. During this follow-up period, patients will have disease assessments performed every 16 weeks (± 1 week). Once patients have exhibited disease progression, they will enter into survival follow-up for assessment of survival only. A new anti-cancer therapy will be reported on the CRF.

Patients will be followed for at least 2 years after first dose of the last patient unless lost to follow-up, consent withdrawal, or study discontinued by the Sponsor, whichever occurs first. Patients will be contacted every 12 weeks (± 4 weeks) for survival status and subsequent anti-cancer treatment.

Patients continuing to experience toxicity at this point following discontinuation of treatment will continue to be followed at least every 4 weeks until resolution or determination, in the clinical judgment of the Investigator, that no further improvement is expected.

For follow-up procedures see Schedule of Activities (Table 1-7).

6.4. Patient Withdrawal

Patients may withdraw from treatment at any time at their own request, or they may be withdrawn at the discretion of the investigator or sponsor for safety, behavioral, or administrative reasons, or the inability of the patient to comply with the protocol-required schedule of study visits or procedures at a given investigative site.

Reasons for discontinuation of study treatment may include:

- CCI [REDACTED]
- Global deterioration of health status requiring discontinuation;
- Unacceptable toxicity (including PML, clinically significant opportunistic infections and tuberculosis);
- Pregnancy;
- Significant protocol violation;
- Lost to follow-up;
- Patient refused further treatment;
- Study terminated by Sponsor;
- Death.

CCI [REDACTED]

[REDACTED]

- [REDACTED]
- [REDACTED]
- [REDACTED]
- [REDACTED]
- [REDACTED]

CCI [REDACTED]

[REDACTED]

7. ASSESSMENTS

Every effort should be made to ensure that the protocol-required tests and procedures are completed as described. However, it is anticipated that from time to time there may be circumstances outside of the control of the investigator that may make it unfeasible to perform the test. In these cases the investigator will take all steps necessary to ensure the safety and well-being of the patient. When a protocol-required test cannot be performed, the investigator will document the reason for this and any corrective and preventive actions that he or she has taken to ensure that normal processes are adhered to as soon as possible. The study team will be informed of these incidents in a timely manner.

For samples being collected and shipped, detailed collection, processing, storage, shipment instructions and contact information will be provided to the investigator site prior to initiation of the study.

7.1. Safety Assessment

Safety assessments will include collection of AEs, SAEs, vital signs and physical examination, neurological examination, ECG (12-lead), laboratory assessments, including pregnancy tests and verification of concurrent medications. A neurological examination will be performed as clinically indicated because of the risk of progressive multifocal leukoencephalopathy with rituximab.

7.1.1. Pregnancy Testing

For female patients of childbearing potential, a serum or urine pregnancy test, with sensitivity of at least 25 mIU/mL, will be performed on 2 occasions prior to starting administration of study treatment: once at the start of screening and once at the baseline visit, immediately before administration of the first dose of study treatment. Following a negative pregnancy test result at screening, appropriate contraception must be commenced and a second negative pregnancy test result will be required at the baseline visit before the patient may receive the investigational product. Pregnancy tests will be repeated at every treatment cycle during the active treatment period, at the end of study treatment, and additionally whenever 1 menstrual cycle is missed or when potential pregnancy is otherwise suspected. Additional pregnancy tests may also be undertaken if requested by institutional review boards (IRBs)/ethics committees (ECs) or if required by local regulations. In the case of a positive confirmed pregnancy, the patient will be withdrawn from administration of investigational product but may remain in the study.

7.1.2. Adverse Events

Assessment of AEs will include the type, incidence, severity (graded by the National Cancer Institute Common Terminology Criteria for Adverse Events [NCI CTCAE] version 4.03) timing, seriousness, and relatedness.

AEs that occur during the study, including baseline signs and symptoms, will be recorded on the AEs CRF page.

7.1.2.1. Adverse Events of Special Interest

Due to pre-clinical results and human experience with compounds of a similar nature, patients should be carefully monitored for endocrine (including but not limited to hypopituitarism and hypoadrenalism) and hepatic events. Evaluation of hypopituitarism or hypoadrenalism should be considered in patients who develop signs and symptoms that may include unexplained loss of body and facial hair, decreased blood pressure, and hyponatremia with hyperkalemia; in the presence of clinical suspicion, laboratory testing should include one or more of the following: thyroid-stimulating hormone (TSH), adrenocorticotrophic hormone (ACTH), and cortisol levels before and 30-60 minutes after corticotropin stimulation. See Study Flowcharts, [Table 3](#), [Table 5](#), and Safety Lab table ([Table 8](#)) for guidance.

John Cunningham virus infection resulting in PML and death can occur in rituximab treated patients with hematologic malignancies. The majority of patients with hematologic malignancies diagnosed with PML received rituximab in combination with chemotherapy or as part of a hematopoietic stem cell transplant. Most cases of PML were diagnosed within 12 months of their last infusion of rituximab. Consider the diagnosis of PML in any patient presenting with new-onset neurologic manifestations. Evaluation of PML includes, but is not limited to, consultation with a neurologist, brain MRI, and lumbar puncture.

7.1.3. Laboratory Safety Assessments

Hematology and blood chemistry ([Table 8](#)) will be drawn at the time points described in the Schedule of Activities ([Table 5](#)) and analyzed at local laboratories.

Blood and/or urine for hematology, chemistry, coagulation, hepatitis B and C, endocrine function, urinalysis and pregnancy testing will be collected at the time points described in the Schedule of Activities, [Table 3](#), and [Table 5](#), and analyzed at local laboratories.

7.1.4. Vital Signs and Physical Examinations

Patients will have a physical exam to include weight, blood pressure, heart rate, body temperature (Portion B only), assessment of ECOG status and height; height will be measured at baseline only. Physical exams will be performed at the time points described in the Schedule of Activities, [Table 3](#) and [Table 5](#).

7.1.5. ECG Assessments

Electrocardiogram (ECG): Triplicate 12-lead (with a 10-second rhythm strip) tracing in the supine position will be used for all ECGs. It is preferable that the machine used has a capacity to calculate the standard intervals automatically. At each time point (see the Schedule of Activities, [Table 3](#), and [Table 5](#)), 3 consecutive ECGs will be performed at approximately 2 minutes apart to determine the mean QTc interval. If the mean QTc is prolonged (>500 msec by any correction method, ie, CTCAE Grade ≥ 3), then the ECGs should be re-evaluated by a qualified person at the site for confirmation as soon as the finding is made, including verification that the machine reading is accurate. If manual reading verifies a QTcF of >500 msec, immediate correction for reversible causes (including electrolyte abnormalities, hypoxia and concomitant medications for drugs with the potential to prolong the QTc interval) should be performed. In addition, repeat ECGs should be

immediately performed hourly for at least 3 hours until the QTc interval resolves to Grade 1 or less. If QTc interval reverts to less than 500 msec, and in the judgment of Investigator(s) and Sponsor is determined to be due to cause(s) other than study drug, treatment may be continued with regular ECG monitoring. If in that timeframe the QTc intervals rise above 500 msec the study drug will be held until the QTc interval decreases to Grade 1 or less. Patients will then re-start the study drug at the next lowest dose level. If the QTc interval has still not decreased to <500 msec after 2 weeks, or if at any time a patient has a QTc interval >515 msec or becomes symptomatic, the patient will be removed from the study. Additional triplicate ECGs may be performed as clinically indicated.

Prior to concluding that an episode of prolongation of the QTc interval is due to study drug, thorough consideration should be given to potential precipitating factors (eg, change in patient clinical condition, effect of concurrent medication, electrolyte disturbance) and possible evaluation by specialist.

If patient experiences a cardiac or neurologic AE (specifically syncope, dizziness, seizures, or stroke), an ECG (triplicate) should be obtained at the time of the event.

If an ECG assessment is matched with PK sampling, the ECG must be carried out before each PK sample drawing such that the PK sample is collected at the nominal time (ie, the timing of the PK collections overrides the timing of the ECG collections).

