Delay of rituximab dosing before Day 1 of Cycle 1: for patients who undergo interruption of dosing of rituximab such that dosing cannot be completed within 24 hours, repeat dosing may be acceptable in certain cases. A repeat of the rituximab dose is contingent upon communication with the Sponsor that, in the opinion of the investigator the patient is a candidate for retreatment, and only if a patient has already received less than 50% of the planned rituximab dose. Repeated dosing of rituximab will only be allowed for Day -7 or Day 0 of Cycle 1 for a maximum of one repeated rituximab infusion, and allowed only if the reasons for interruption do not include persistence of a Grade 3 or Grade 4 AE attributed to rituximab.

Delay of rituximab dosing after Day 1 of Cycle 1: Patients who have dose interruptions of rituximab that preclude completion of the infusion within 24 hours will permanently discontinue the study treatment, including treatment with PF-05082566.

Patients who develop progressive multifocal leukoencephalopathy (PML) should permanently discontinue study treatment (see [Section 7.1.2.1](#) for more details).

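### Protocol Section 7.1.5 takes patients with marked QTc prolongation out of the study, although Section 6.3 has no toxicity exit from follow-up and the other toxicity rules end treatment only

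*Protocol*

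**What the plan says.** Protocol Section 7.1.5 sets out graded actions for a prolonged QTc: re-evaluate the tracing, correct reversible causes, repeat the ECG, hold the drug, restart one dose level lower. The last step covers three situations: QTc still not below 500 msec after 2 weeks, QTc above 515 msec at any time, or symptoms. In each of them (the text runs on from 515) "msec or becomes symptomatic, the patient will be removed from the study". The sentence does not say whether follow-up continues.

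Protocol Section 6.3 says "Patients will be followed for at least 2 years after first dose of the last patient unless lost to follow-up, consent withdrawal", or the sponsor stops the study. It sends patients without progression at the end of treatment to disease assessments every 16 weeks, and it contacts patients every 12 weeks for survival. For unresolved toxicity it says "Patients continuing to experience toxicity at this point following discontinuation of treatment will continue to be followed at least every 4 weeks", until the event resolves or the investigator expects no further improvement. Footnote 23 of Table 5 likewise continues adverse event follow-up until drug-related toxicity has resolved, if that is later than 28 days after the last dose.

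**The concern.** A patient with unresolved QTc prolongation is covered by two instructions that cannot both be followed. Section 7.1.5 takes the patient out of the study; Section 6.3 and Table 5 footnote 23 keep the patient under observation because the toxicity has not resolved. A site that follows Section 7.1.5 to the letter stops observing a patient with one of the most marked QTc findings, in a study where QTc is a named secondary endpoint.

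The efficacy data are affected too. Follow-up would end because of a finding that may be caused by the drug, so the resulting censoring of PFS, DR and OS may be informative. In Portion A, a patient removed after a first response but before its confirmation would not count as a responder.

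**Working it through.** **Step 1. Compare the exit rules.**

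| Trigger | Protocol section | What ends |
|---|---|---|
| QTc not below 500 msec after 2 weeks, above 515 msec, or symptoms | 7.1.5 | the study |
| Progressive multifocal leukoencephalopathy | 5.4 | treatment: "should permanently discontinue study treatment" |
| Toxicity not recovered after an 8-week delay | 5.4.3 | treatment: "the patient will be permanently discontinued from study treatment" |
| More than 2 dose reductions | 5.4.4 | treatment, with follow-up stated: "will be permanently discontinued from the study treatment and entered into the follow-up phase" |
| Reduction needed at 0.24 mg/kg | 5.4.4 | treatment |
| Unacceptable toxicity | 6.4 | treatment; listed under "Reasons for discontinuation of study treatment may include" |
| Pregnancy (not a toxicity) | 7.1.1 | product only: "the patient will be withdrawn from administration of investigational product but may remain in the study" |

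QTc is the only toxicity whose visible rule ends study participation. The pregnancy rule shows that the protocol can separate stopping the product from leaving the study.

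**Step 2. Trace the literal rule through the SAP.**

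- *Response, Portion A.* SAP Section 6.2.2.1 requires two determinations at least 4 weeks apart, and patients who drop out before reaching a response count as non-responders. Removal between the first and the confirming scan turns a possible responder into a non-responder. With about 20 melanoma patients per dose (Protocol Section 9.3), one patient is 1/20 = 5 percentage points of ORR. Portion B does not require confirmation.
- *PFS and DR.* Without an event, both are censored at the last adequate tumor assessment (SAP Sections 6.2.2.3 and 6.2.2.5). SAP Table 4 has no category for removal under the protocol. A removed patient with an adequate post-baseline scan and no event falls to the last row, *Ongoing without an event*.
- *OS.* It is censored at last contact (SAP Section 6.2.2.6). SAP Table 5 labels the patient *Lost to follow-up* once last contact is more than 16 weeks before the cut-off.
- *Serious adverse events.* Reporting to 60 days after the last dose (Protocol Section 8.2) is tied to dosing and is not lost.

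**Step 3. Count the visits lost in one example.** Take the last-enrolled patient, removed after the Cycle 2 Day 1 dose and ECG, who still attends the End of Treatment visit.

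- Cycle 2 Day 1 is Day 29, so week 4.
- End of Treatment is about 28 days after the last dose: 4 + 4 = week 8.
- The 2-year minimum is week 104, so 104 − 8 = 96 weeks remain.
- Without progression: 96/16 = 6 disease assessments.
- With progression already documented: 96/12 = 8 survival contacts.
- In either case, toxicity visits at least every 4 weeks until resolution are also lost.

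Progression or death lowers these counts. For a patient enrolled *g* weeks before the last one, the remaining time is 96 + *g* weeks, because Section 6.3 counts from the last patient's first dose.

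**Step 4. Ask how often this would happen.** The documents give no QTc event rate. Protocol Section 1.4 reports 133 treated patients to June 2016. The treatment-related Grade 3 events were hyponatremia and fatigue in Portion A, and Portion B had no related event of Grade 3 or higher. This suggests few cases, but it gives no rate for Section 7.1.5, which applies whatever the cause of the prolongation.

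**The case against.** The strongest reply is that the phrase means off study drug. It closes a sequence of dosing actions, and the protocol often says study when it means treatment. Section 3.3.1 counts progression as a reason for dropping out of the study, yet progressed patients go on to survival follow-up. Section 7.2.1 samples patients who end the study at the End of Treatment visit. Section 3.3.1.1 is the clearest: Japan-cohort patients who discontinue from the study may still be observed off study. The follow-up rules in Section 6.3 are also unconditional, and parts of Section 6.4, which governs withdrawal, are redacted.

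Most of this stands, and it makes a wording slip the likelier explanation. A reader might infer that the sponsor means to abandon follow-up of these patients; the documents do not support that. But the reply does not remove the conflict. Section 7.1.5 refers to treatment and study drug at the earlier steps and changes to the study only at removal, so a site could take the change as deliberate. The visible text of Section 6.4 does not settle it.

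A reader might also infer that these patients would be invisible in the reporting. That goes too far. SAP Section 6.5.2.1 tabulates discontinuation of study drug and of the study by main reason, and SAP Section 6.6.1.2 tabulates and lists adverse events leading to discontinuation. Only the censoring categories in SAP Tables 4 and 5 lack a matching entry.

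**Conclusion.** The inconsistency is real and of low severity. Section 7.1.5, read as written, conflicts with Section 6.3 and with Table 5 footnote 23, and it is out of line with every other visible toxicity exit. It is probably a slip, and harm arises only if sites apply it literally.

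The effect on results should be small. Few cases are expected, SAP Section 5.1.1 plans no hypothesis test, and PFS, DR and OS are descriptive. The counts of 6 disease assessments and 8 survival contacts assume the last-enrolled patient, removal after Cycle 2 Day 1, and an End of Treatment visit that still takes place. They should not be read as the most that any patient could lose, since patients enrolled earlier have longer follow-up at stake.

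Because Section 7.1.5 mentions both any correction method and a manually read QTcF, a reader might infer that the 500 and 515 msec limits should be confined to a verified QTcF. The documents do not support this. The QTcF reading appears only at the step that prompts correction of reversible causes, and confining the limits to it would narrow a safety stop for reasons unrelated to the follow-up conflict.

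**What to change.** In Protocol Section 7.1.5, replace removal from the study with permanent discontinuation of study treatment and entry into follow-up per Section 6.3. This follows the model already used in Section 5.4.4. Leave the QTc thresholds and the correction method unchanged.

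The cost is one phrase in the next amendment. The follow-up visits already exist, dosing still stops at the same point, and no SAP change is needed, because patients who stay in follow-up are handled by the existing censoring rules.
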